## 10.3.1 Safety Reporting to Investigators, IRBs or IECs, and Regulatory Authorities

The sponsor will be responsible for reporting all suspected unexpected serious adverse reactions (SUSARs) and any other applicable SAEs to regulatory authorities, including investigators and IRBs or IECs, as applicable, in accordance with national regulations where the study is conducted. Relative to the first awareness of the event by/or further provision to the sponsor or sponsor's designee, SUSARs will be submitted to the regulatory authorities as expedited report within 7 days for fatal and life-threatening events and 15 days for other serious events, unless otherwise required by national regulations. The sponsor will also prepare an expedited report for other safety issues where these might materially alter the current benefit:risk assessment of an investigational medicinal product or that would be sufficient to consider changes in the investigational medicinal products administration or in the overall conduct of the trial. The investigational site also will forward a copy of all expedited reports to his or her IRB or IEC in accordance with national regulations.

# 11.0 STUDY-SPECIFIC COMMITTEES

No steering committee, data safety monitoring committee, or clinical endpoint committee will be used in this study.

#### 12.0 DATA HANDLING AND RECORDKEEPING

The full details of procedures for data handling will be documented in the Data Management Plan. AEs, PTEs, medical history, and concurrent conditions will be coded using the Medical Dictionary for Regulatory Activities (MedDRA). Drugs will be coded using the World Health Organization (WHO) Drug Dictionary.

### 12.1 CRFs (Electronic)

Completed eCRFs are required for each subject who signs an informed consent.

The sponsor or its designee will provide investigative sites with access to eCRFs. The sponsor will make arrangements to train appropriate site staff in the use of the eCRF. These forms are used to transmit the information collected in the performance of this study to the sponsor and regulatory authorities. eCRFs must be completed in English.

After completion of the entry process, computer logic checks will be run to identify items, such as inconsistent dates, missing data, and questionable values. Queries may be issued by Takeda personnel (or designees) and will be answered by the site.

Corrections to eCRFs are recorded in an audit trail that captures the old information, the new information, identification of the person making the correction, the date the correction was made, and the reason for change.

The principal investigator must review the eCRFs for completeness and accuracy and must sign and date the appropriate eCRFs as indicated. Furthermore, the investigator must retain full responsibility for the accuracy and authenticity of all data entered on the eCRFs.

After the lock of the clinical study database, any change of, modification of or addition to the data on the eCRFs should be made by the investigator with use of change and modification records of the eCRFs (Data Clarification Form) provided by the sponsor. The principal investigator must review the data change for completeness and accuracy, and must sign, or sign and seal, and date.

The eCRFs will be reviewed for completeness and acceptability at the study site during periodic visits by study monitors. The sponsor or its designee will be permitted to review the subject's medical and hospital records pertinent to the study to ensure accuracy of the eCRFs. The completed eCRFs are the sole property of the sponsor and should not be made available in any form to third parties, except for authorized representatives of appropriate governmental health or regulatory authorities, without written permission of the sponsor.

#### 12.2 Record Retention

The investigator agrees to keep the records stipulated in Section 12.1 and those documents that include (but are not limited to) the study-specific documents, the identification log of all participating subjects, medical records, temporary media such as thermal sensitive paper, source worksheets, all original signed and dated informed consent forms, subject authorization forms regarding the use of personal health information (if separate from the informed consent forms),

electronic copy of eCRFs, including the audit trail, and detailed records of drug disposition to enable evaluations or audits from regulatory authorities, the sponsor or its designees. Any source documentation printed on degradable thermal sensitive paper should be photocopied by the site and filed with the original in the subject's chart to ensure long term legibility. Furthermore, International Conference on Harmonisation (ICH) E6 Section 4.9.5 requires the investigator to retain essential documents specified in ICH E6 (Section 8) until at least 2 years after the last approval of a marketing application for a specified drug indication being investigated or, if an application is not approved, until at least 2 years after the investigation is discontinued and regulatory authorities are notified. In addition, ICH E6 Section 4.9.5 states that the study records should be retained until an amount of time specified by applicable regulatory requirements or for a time specified in the Clinical Study Site Agreement between the investigator and sponsor.

Refer to the Clinical Study Site Agreement for the sponsor's requirements on record retention. The investigator should contact and receive written approval from the sponsor before disposing of any such documents.

#### 13.0 STATISTICAL METHODS

### 13.1 Statistical Analysis Plan

A statistical analysis plan (SAP) will be prepared and finalized prior to unblinding of subject's treatment assignment. This document will provide further details regarding the definition of analysis variables and analysis methodology to address all study objectives.

A blinded data review will be conducted prior to unblinding of subject's treatment assignment. This review will assess the accuracy and completeness of the study database, subject evaluability, and appropriateness of the planned statistical methods.

### 13.1.1 Analysis Sets

#### Total Set

The total set consists of all subjects who signed the informed consent form including subjects withdrawn prior to randomization (defined as not randomized subjects).

### Full Analysis Set

This will consist of all subjects randomized to receive study treatment whether or not they received treatment. Subjects will be assigned to the randomized treatment group regardless of treatment received.

#### Per-Protocol Analysis Set

The Per-Protocol (PP) population will consist of subjects in the FAS with the additional following criteria for exclusion:

- Did not receive study treatment as per randomization schedule.
- Dose of randomized treatment was not adjusted.
- Violated inclusion criteria, such as:
  - Does not have a history of constipation defined as SBM frequency of less than 3 times per week on average for 6 months or longer (and observed during Screening Period).
  - Does not have SBMs with ≥1 of the following 3 symptoms for the last 6 months or longer, in at least 1 out of every 4 bowel movements: scybalum stool or hard feces, straining, or the sensation of incomplete evacuation.
  - The subject rarely has loose stools without the use of laxatives.
- Violated exclusion criteria, such as:
  - The subject has a history or clinical manifestations of significant mechanical obstruction (intestinal obstruction due to tumor, hernia etc).

### CONFIDENTIAL

- Has chronic constipation due to a secondary cause (medications, diabetes mellitus, hypothyroidism, depression, etc).
- Has sufficient criteria for IBS or there is a functional defecation disorder.
- SBM frequency is 3 or more per week.
- SBM frequency has been less than 3 times per week for less than 6 months in duration or whose symptoms associated with SBM have been present for less than 6 months (hard feces, sensation of incomplete evacuation, or straining).
- Received treatment with a rescue medication within 24 hours prior to the first dose on the morning of Day 1.
- Has megacolon/megarectum or has received a diagnosis of intestinal pseudo-obstruction.
- Has confirmed or suspected organic disorders of the large intestine (obstruction, stenosis, carcinoma, or inflammatory bowel disease). Any subject in whom total colonoscopy has detected a polyp requiring treatment is excluded from this study.
- Has been hospitalized for gastrointestinal or abdominal surgery within 3 months before the start of this study.
- Use of any excluded medications, procedures or treatments prior to the assessment of the primary endpoint.

Any other significant event interfering with efficacy evaluation of primary endpoint, to be decided at the Targeted Data Review Meeting.

Subjects will be assigned to the treatment group dependent upon the actual treatment randomized and received.

#### Safety Analysis Set

This will consist of all subjects who receive study treatment. Subjects will be assigned to the treatment group dependent upon the actual treatment received.

The analysis populations must be identified before database lock by the Responsible Medical Officer, the Coordinating Study Manager and the Study Statistician. The reason(s) for exclusion of subjects from the analysis populations must be documented, signed and filed in the Trial Master File (TMF).

The FAS will be used for efficacy analyses. Supportive analyses based on the PP will be performed for the primary efficacy variable. Definitions of criteria constituting major deviations will be provided, prior to unblinding.

### 13.1.2 Analysis of Demographics and Other Baseline Characteristics

Demographic and other baseline characteristics will be summarized descriptively.

## 13.1.3 Efficacy Analysis

Two-sided tests at a significance level of  $\alpha$ =5% will be used throughout unless otherwise stated. The null hypothesis is that lubiprostone is equal to placebo against the alternative that lubiprostone is different to placebo. All analyses will be performed using the FAS. Analyses specified for the PP are to be regarded as supportive evidence. There will be no adjustment for multiplicity.

All efficacy endpoints will be summarized by treatment and visit. If baseline measures are also defined and collected for an efficacy endpoint then change from Baseline at each visit will also be presented by summary statistics by treatment and visit. Baseline is defined as the last recorded measurement prior to treatment. For parameters based on diary data, baseline values will be derived using the data from the Screening Period.

Centers may be pooled geographically if necessary for analysis purposes.

The LOCF technique will be used to impute missing values. For a given subject, the most recent nonmissing treatment-period data point will be carried forward to the subsequent week where data are missing. Supportive analyses will be conducted without missing value imputation (ie, without LOCF) and with a 'worse-case' scenario where missing values are assigned the worst case values recorded in the study by any subject for that endpoint at that time.

# 13.1.3.1 Primary Endpoint

The primary endpoint for the study is the frequency of SBM at Week 1. An SBM is defined as any BM that does not occur within 24 hours after rescue medication use. The SAP will contain more details on the handling of rescue medication and missing or partial data.

In order to adjust for early withdrawals, weekly SBM frequency rates will be calculated as follows:

(Number of SBMs / Number of Days) 
$$\times$$
 7

The number of days in the denominator above is the number of days during the week that the subject was in the study. Weeks will be calculated as 168-hour intervals starting with the exact time of the first intake of study drug. The number of days will generally be 7 unless a subject drops out during a treatment week. If the number of days is less than 4, then the data will be considered insufficient and the rate will be set to missing.

The primary endpoint will be analyzed using van Elteren's test stratified by center to examine the difference between lubiprostone and placebo. Additionally the endpoint will be analyzed using analysis of variance (ANOVA) models with center and treatment in the model as a sensitivity analysis. The estimated least squares (LS) means, related mean difference and associated 95% CI will also be presented to aid interpretation of the clinical effect. The interaction between treatment and center will also be examined in a separate ANOVA model.

This endpoint will be analyzed for the FAS. A sensitivity analysis using the PP will also be presented.

To examine the effects of any dose reduction in response to an AE an additional sensitivity analysis will also be performed. This will be performed on the FAS where data from those subjects with a dose reduction will be excluded from the time of dose reduction and subjects will be treated as a drop-out from this time point onwards. Additionally, another factor will be added to the ANOVA model to examine the effect of dose reduction, this will be performed on the FAS, with no subjects excluded.

## 13.1.3.2 Secondary Endpoints

All secondary endpoints will be analyzed for the FAS only.

## SBM Frequency at Week 2, 3 and 4

The secondary endpoint will be analyzed as specified for the primary endpoint separately for each week.

## Proportion of Subjects With an SBM Within 24 hours After First Dose

The proportion of subjects with an SBM within 24 hours after first dose in Week 1 will be analyzed by a Cochran-Mantel-Haenszel (CMH) test stratified by center. Additionally a logistic regression model will be used with treatment and center as factors as a sensitivity analysis. The estimated odds ratio and associated 95% CI will also be presented to aid interpretation of the clinical effect. The interaction between treatment and center will not be examined in a separate model

#### Mean Degree of Straining (Week 1, 2, 3, and 4)

For each subject, the mean degree of straining will be averaged for all SBMs in a given week. The mean degree of straining will then be analyzed by van Elteren tests, stratified by center, at Weeks 1, 2, 3, and 4 separately. Additionally the endpoint will be analyzed using ANOVA models with center and treatment in the model as a sensitivity analysis.

## Mean Degree of Stool Consistency (Week 1, 2, 3, and 4)

Stool consistency will be analyzed in the same manner described for the degree of straining.

## Weekly Abdominal Symptoms Score (Bloating and Discomfort) (Week 1, 2, 3, and 4)

The abdominal symptoms (bloating and discomfort upon waking in the morning) will be analyzed separately by van Elteren tests, stratified by center, at Weeks 1, 2, 3, and 4. Additionally a cumulative logistic regression model will be used with treatment and center as factors as a sensitivity analysis. The estimated odds ratio and associated 95% CI will also be presented to aid interpretation of the clinical effect. The interaction between treatment and center will also be examined in a separate model.

## Weekly Responder Rate (Week 1, 2, 3, and 4)

Weekly responder rate (non-responder/ moderate responder/ full responder) will be analyzed by van Elteren tests, stratified by center, at Weeks 1, 2, 3, and 4 separately. Additionally a cumulative logistic regression model will be used with treatment and center as factors as a sensitivity analysis. The estimated odds ratio and associated 95% CI will also be presented to aid interpretation of the clinical effect. The interaction between treatment and center will also be examined in a separate model. A non-responder will be defined as any subject with a spontaneous BM frequency rate of less than 3 for a given week, any subject who dropped out during or prior to the given week due to lack of efficacy, or any subject who used rescue medication during or within 24 hours prior to the given week. Otherwise, the subject will be considered a responder. A responder with a spontaneous BM frequency rate  $\geq$  3 but <4 will be considered a moderate responder. Otherwise, the subject will be a full responder ( $\geq$  4 SBM).

### 13.1.3.3 Additional Endpoints

#### **Efficacy**

PAC-QOL Questionnaire: The PAC-QOL will be analyzed separately for the first 24 items that comprise the Dissatisfaction Index and for the last 4 items that comprise the Satisfaction Subscale at Baseline, and at Weeks 2 and 4.

The Dissatisfaction Index will be analyzed using van Elteren's test stratified by center to examine the difference between lubiprostone and placebo. Additionally the endpoint will be analyzed using ANOVA models with center and treatment in the model as a sensitivity analysis. The estimated LS means, related mean difference and associated 95% CI will also be presented to aid interpretation of the clinical effect.

The Satisfaction Index will be categorized by combined scores of the 4 items as either poor (0-4), fairly good (5-8), good (9-12), or excellent (13-16) and will be analyzed by van Elteren tests, stratified by center, at Baseline, and at Weeks 2 and 4 separately. Additionally a cumulative logistic regression model will be used with treatment and center as factors as a sensitivity analysis. The estimated odds ratio and associated 95% CIs will also be presented to aid interpretation of the clinical effect.

#### Safety

Adverse events will be summarized using the safety analysis set. No statistical testing or inferential statistics will be generated.

All AEs will be coded using the MedDRA. Data will be summarized using preferred terms (PTs) and primary system organ class (SOC).

Vital signs, clinical laboratory values, and body weight will be summarized by treatment group for both actual and change from baseline values.

## 13.1.3.4 Exploratory Endpoint

No interim analysis is planned.

### 13.3 Determination of Sample Size

Assuming equal allocation, a power of 90%, an alpha level of 0.05 for a 2-sided test, a placebo mean of 4 (standard deviation of 2.7), and a treatment mean of 5.9 (standard deviation of 4) for SBM frequency at Week 1 and using the Wilcoxon-Mann-Whitney test, a total sample size of 146 is required. The Wilcoxon-Mann-Whitney test is a non-parametric test of the null hypothesis that the distribution is the same for both placebo and treatment responses against the alternative that there is a location difference between the 2. The estimates of placebo and treatment response are based on a previous study conducted by Sucampo Pharmaceuticals in the US (Protocol No. RTU/0211SC0131).

The primary endpoint requires subjects to complete at least 4 days of the study diary, therefore assuming a drop-out rate of 3% by Day 4 an additional 4 subjects are required, giving a total of 150 subjects.

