Approximately 150 subjects whose constipation is confirmed during the Screening Period will be randomized in the Double-Blind Treatment Period to receive either lubiprostone or matching placebo BID. Others whose constipation does not satisfy the criteria during the 14-day Screening Period or those who receive a rescue medication within 24 hours prior to the first dose on Day 1 are ineligible for randomization in the Double-Blind Treatment Period and therefore will be excluded from the study. Subjects who satisfy the inclusion criteria and do not meet the exclusion criteria are randomized to 1 of the treatment groups in the order of the number assigned. Approximately 150 subjects with CIC will be randomized to 2 groups: active treatment or placebo in a 1:1 ratio (75 subjects each) in a double-blinded manner.

[figure not shown]
Subjects will be instructed to take 1 capsule BID, orally, at the same time of day, preferably in the morning with breakfast and in the evening with dinner. Subjects are to begin their study drug treatment in the morning with breakfast following Visit 2.

Subjects will return to the study site on approximately Study Days 8, 15, and 29 during the 4 weeks of double-blind treatment and will be followed for an additional 2 weeks during the Follow-Up Period, in which no treatment will be administered.

At the investigator's discretion, with consideration to subject's bowel movement frequency and consistency, dose adjustments (dose reduction) may be made in a double-blind manner. Dose adjustment should be documented in the subject's source notes. Procedure for reduction of study drug dose due to Adverse Events is described in Section 7.7.

Subjects who withdraw prematurely will be seen within 1 week of discontinuation for an Early Termination Visit. A schematic of the study design is included as Figure 6.a. A schedule of assessments is listed in Appendix A.

Figure 6.a Schematic of Study Design

Note: Randomization occurs on Day -1 of the Screening Period. The first dose of study drug is administered the next day, on Day 1 of the Double-Blind Treatment Period.

Note: There is no treatment during the Follow-up Period.

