# 6.0 DETERMINATION OF SAMPLE SIZE

Assuming equal allocation, a power of 90%, an alpha level of 0.05 for a 2-sided test, a placebo mean of 4 (standard deviation of 2.7), and a treatment mean of 5.9 (standard deviation of 4) for SBM frequency at Week 1 and using the Wilcoxon-Mann-Whitney test [1], a total sample size of 146 is required. The Wilcoxon-Mann-Whitney test is a non-parametric test of the null hypothesis that the distribution is the same for both placebo and treatment responses against the alternative that there is a location difference between the two. The primary analysis will be conducted using the van Elteren test, which is a stratified version of the Wilcoxon-Mann-Whitney test, use of the Wilcoxon-Mann-Whitney test for sample size estimation will provide an approximate sample size for the van Elteren analysis. The estimates of placebo and treatment response are based on a previous study conducted by Sucampo Pharmaceuticals in the United States of America (Protocol No. RTU/0211SC0131).

The primary endpoint requires subjects to complete at least 4 days of the study diary, therefore assuming a non-evaluable rate of 3% by Day 4 an additional 4 subjects are required, giving a total of 150 subjects.

1 5

	CROSS-REGIONAL TEMP	LATE	
Template Number:	C-TMPL-DO-801	Page:	12 of 31
Version Number:	1.2	Effective Date:	14 Sep 201
This version replaces	s: 1.1		
Parent Document:	C-SOP-DO-800		
Template Title:	Statistical Analysis Plan (Legacy Takeda)	)	

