As the primary endpoint is within the first week of study treatment and only 4 days of diary collection are required it is not anticipated that missing values should be a cause of concern therefore the LOCF technique will be used to impute missing values for efficacy analysis purposes only. For a given subject, the most recent nonmissing data point will be carried forward to the subsequent week where data are missing. Details for each efficacy parameter are given below. It is expected, based on previous studies, that the number of subjects with in-sufficient post baseline data for the primary endpoint will be small therefore a simple approach to handling missing data will be used. Where there is no post baseline efficacy data then the baseline value will be used, it is expected that the number of SBMs should increase for those on treatment, therefore using a baseline value for missing post baseline data assumes no treatment effect, this approach can be considered conservative,. To examine the effect of the requirement to have at least a minimum of 4 days post baseline efficacy data for the primary endpoint, using the stratified van Elteren test [2], will be conducted using all valid SBM data post baseline even when less than 4 days data is present, only where there is no post baseline data will baseline be used in this analysis.

An SBM is defined as any BM that does not occur within 24 hours after rescue medication use. Certain periods after taking rescue medication will be defined as "blackout periods" during which BMs are considered as non-spontaneous. Blackout periods, including those with missing or partial times for rescue medication use in the diary, will be handled as follows:

0-24 hours post rescue medication intake if the time is fully specified.

0-24 hours post rescue medication intake if the hour is present, but the minute is missing. The blackout time will commence from the imputed time. If the minutes are incomplete or missing from either the rescue medication or bowel movement entry then it is assumed that the missing values are zero and an imputed time will be calculated. e.g.

1	5	_	_	=	1	5	0	0
2	1	5		=	2	1	5	0

0-48 hours, beginning from midnight on the day the rescue medication intake is recorded for, if the hour is missing from the time entry for the rescue medication.

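### SAP 6.0 keeps a 4-subject allowance that the baseline fill in SAP 7.8 largely undoes: on the plan's own model 150 subjects give about 87-89% power, not 90%

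*Protocol*

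**What the plan says.** Protocol 13.3 sizes the trial with a Wilcoxon-Mann-Whitney test on Week 1 SBM frequency: placebo 4 (SD 2.7), lubiprostone 5.9 (SD 4), 90% power, "an alpha level of 0.05 for a 2-sided test", 146 subjects in total. Because the endpoint needs at least four diary days, it adds: "assuming a drop-out rate of 3% by Day 4 an additional 4 subjects are required, giving a total of 150 subjects". SAP 6.0 repeats the calculation but renames the loss: "assuming a non-evaluable rate of 3% by Day 4 an additional 4 subjects are required".

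The primary test is run on the full analysis set (FAS), which Protocol 13.1.1 defines as follows: "This will consist of all subjects randomized to receive study treatment whether or not they received treatment". SAP 7.2 has the same definition, and SAP 7.8.1 applies the van Elteren test to that set. Both documents set the Week 1 frequency to missing when there are fewer than 4 days (Protocol 13.1.3.1, SAP 7.8.1).

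They differ on what follows. Protocol 13.1.3 carries forward treatment-period values only. SAP 7.8 omits that limit and adds: "Where there is no post baseline efficacy data then the baseline value will be used". It describes this as conservative because it assumes no treatment effect.

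**The concern.** An allowance for non-evaluable subjects tops up the number who enter the test. It works when the missing subjects leave, since the remaining sample still has the planned contrast. It does not work when they stay in at a value unrelated to treatment. The sample is then nominally complete, but part of each arm sits at the same low level and the difference between arms shrinks.

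SAP 6.0 treats the 3% as leaving, while SAP 7.8 appears to keep them. If so, the stated 90% does not describe the primary analysis that will be run. This is separate from any loss due to stratifying by center, which SAP 6.0 covers only by calling the sample size approximate for the van Elteren test.

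**Working it through.** **Who is filled.** Read alone, the SAP 7.8 sentence covers only subjects with no post-baseline data. The next sentence describes an additional analysis that uses whatever data exist under four days and confines the baseline fill to subjects with none. That restriction has a purpose only if the primary analysis fills more widely, that is, also for subjects with 1 to 3 days. The worst-case analysis in SAP 7.8.1 likewise counts subjects under four days as missing.

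**Inputs.** The means, SDs, alpha, test, 146, 150 and 3% come from Protocol 13.3, and 75 per arm from Protocol 6.1. The baseline level is an assumption: mean 1.28 to 1.68 with SD 0.77 to 0.88, from Table 4.a, capped below 3 per week. The SD of 1.32 listed for SC0131 was not run. Missingness is taken as equal in both arms.

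**Step 1: reproduce the plan.**
- P = Phi(1.9 / sqrt(2.7² + 4²)) = Phi(0.394) = 0.653.
- Noether: N = (1.960 + 1.282)² / (3 × 0.1531²) = about 149.
- Simulation with normal outcomes, 73 per arm: 89.8-90.3% power. The 146 reproduces.
- 146 / 0.97 = 150.5, so 150 is right to within rounding.

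**Step 2: mix in the baseline fill.** Take baseline 1.5 (SD 0.8) and a fraction of 0.03 in each arm.
- P(lubiprostone > baseline) = Phi(4.4 / sqrt(16 + 0.64)) = 0.860.
- P(baseline > placebo) = Phi(-2.5 / sqrt(7.29 + 0.64)) = 0.187.
- P* = 0.97² × 0.6531 + 0.03 × 0.97 × (0.860 + 0.187) + 0.03² × 0.5 = 0.6454.
- The excess over 0.5 falls from 0.1531 to 0.1454, a ratio of 0.95.
- Noether power at 150: Phi(sqrt(3 × 150) × 0.1454 - 1.960) = 87.0%, against 90.1% with none missing.

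**Step 3: simulation**, 20,000 to 60,000 trials per scenario (Monte Carlo standard error about 0.1 to 0.2 points). Ranges are across repeated runs and baseline values.

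| 75 per arm | Power |
|---|---|
| None missing | 90.5-90.6% |
| 3% removed from the test | 89.6-90.0% |
| 3% kept at baseline, at random | 87.4-88.0% |
| Exactly 2 per arm kept at baseline | 88.0-89.0% |
| 1 per arm kept at baseline, no other loss | 89.7-89.9% |

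The second row is what the allowance assumes, and there it works. The third and fourth rows are what SAP 7.8 does on the wider reading. The last row illustrates the narrow reading.

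**Step 4: sensitivity.**
- Unequal splits matter more than the baseline level. With 1 placebo and 3 lubiprostone subjects filled, power is about 84%; with 0 and 4, about 79%; with 4 and 0, about 94%.
- Other outcome shapes, none missing against 3% filled at 75 per arm: gamma 89.6% to 86.2%, negative binomial 86.7% to 83.7%, lognormal 96.3% to 94.6%. The loss is 1.7 to 3.4 points in each case, but the absolute level moves far more.
- A van Elteren test with 10 random centers (4,000 trials): 85.8% to 82.8%, a similar loss on top of stratification.
- For scale only: 146 / 0.95² = about 162 subjects would hold 90% with the fill. Simulation and Noether together give about 160-166.

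**The case against.** **The Protocol is consistent with itself.** Its LOCF rule uses treatment-period data only, so a missing Week 1 value has nothing to carry forward, the subject leaves the test, and the extra 4 do their job. This stands. A reader might infer that the arithmetic in Protocol 13.3 is wrong; it is not. The mismatch arises in the SAP, which adds a fill and keeps an allowance built for a different rule. SAP 7.13 does not record that change.

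**The wider fill is an inference.** The quoted SAP sentence speaks of subjects with no post-baseline data, and a subject with 1 to 3 days has some. The following sentence supports the wider reading strongly but does not state it. On the narrow reading power stays close to 90%. The conclusion therefore has to be conditional, and the text needs settling.

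**The loss is small beside the uncertainty in the inputs.** This also stands. Outcome shape alone moves the filled power from 83.7% to 94.6%. The SC0131 row of Table 4.a (3.46 ± 2.28 against 5.69 ± 4.41), the study that the plan names as its source, gives 93.8% with the same 3% fill; the SC0831 row gives over 99.9%. A reader might infer that the trial is underpowered or needs more subjects. The documents do not support that.

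**Shrinking the mean difference alone costs almost nothing.** Scaling 1.9 by 0.97 gives 1.84, and an efficiency-adjusted t calculation then gives 89.2-90.0%. But this understates the loss for a rank test, because the filled values fall among the lowest ranks.

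**The SAP already calls the fill conservative and expects few cases.** That defends the choice of fill. It does not make the power statement match it.

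**Conclusion.** The point holds as a mismatch between SAP 6.0 and SAP 7.8. If all subjects with fewer than 4 days enter the FAS test at baseline, 150 subjects give about 87-89% power on the plan's own model, 1 to 3 points under 90% and before any loss from stratification. This rests on normal outcomes at the stated means and SDs, an unstratified Wilcoxon-Mann-Whitney test, about 3% non-evaluable with equal rates in the two arms, and an assumed baseline of about 1.3 to 1.7. The baseline level hardly matters within that range; an unequal split would. The result is a power statement that the planned analysis does not quite deliver. It does not call for a larger trial.

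**What to change.** - **SAP 6.0:** keep 150. Restate the power as about 87-89% for the stated means, SDs and 3% rate when those subjects stay in the FAS at baseline, with the baseline assumption given and any stratification loss stated separately. Drop the statement that 4 additional subjects offset the 3%, and stop calling these subjects non-evaluable.
- **SAP 7.8:** say explicitly that in the primary analysis the baseline fill applies to every subject with fewer than 4 days in Week 1. If the narrow reading is what is meant, say that instead and how subjects with 1 to 3 days are handled; the power statement can then stay close to 90%.
- **Protocol 13.3** (and the same sentence in the Section 2.0 summary): add a cross-reference to the SAP figure, noting that the Protocol's own LOCF rule does not contain the fill.
- **SAP 7.13:** record the fill as a change from the Protocol's missing-data rule.

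The cost is a few sentences and a slightly less favourable power figure. No subjects, endpoints or procedures change.
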